6.1.5 Time Period for Adverse Events

For purposes of this study, events that occur following randomization through the last study visit will be reported as adverse events. Serious adverse events, unexpected medically attended events, and new onset chronic illnesses will be recorded from randomization through twelve months after the last study dose. Specifically, events that occur following consent to participate in the study, but prior to actual randomization, are not adverse events. These should be recorded as baseline conditions.

6.1.6 Data Collection Procedures for Adverse Events

After patient randomization all adverse events (including serious adverse events) will be recorded according to relatedness, severity, and expectedness, as well as their duration and any treatment prescribed. Any medical condition present at the time of randomization, recorded in the patient's baseline history at study entry, which remains unchanged or improves (unless the clinician feels it is clinically relevant), will not be recorded as an adverse event at subsequent evaluations. However, worsening of a medical condition that was present at the time of randomization will be considered a new adverse event and reported.

Adverse events will be coded using the MedDRA coding vocabulary. Coding will be done centrally at the Data Coordinating Center as this requires specific training.

6.1.7 Unanticipated Problems (UP)

Unanticipated problems (UP) are defined as incidents, experiences, or outcomes that are unexpected, related or possibly to participation in the study, and suggest that the research places subjects at a greater risk of harm than was previously known or recognized. The site investigator will report unanticipated problems to the Data Coordinating Center within 24 hours of becoming aware of the event. A detailed completed report will be required to be sent to the Data Coordinating Center within 3 working days of the event. After receipt of the complete report, the Data Coordinating Center will report these unanticipated problems to the CTRM in an expedited manner (as close to 24 hours as possible).

In accordance with local IRB requirements, the site investigator may be required to report such unanticipated problems to the IRB in addition to notifying the Data Coordinating Center. In the event that the medical monitor believes that such an event warrants emergent suspension of enrollment in the trial, and funding staff cannot be reached expeditiously, the Data Coordinating Center will notify the study investigator and all site investigators to cease enrollment in the trial.

6.1.8 Monitoring Serious Adverse Events

A qualified physician will be designated to fulfill the function of the medical monitor for this study. Site investigators and/or research coordinators will report serious adverse events to the Data Coordinating Center within 24 hours of becoming aware of the event. A detailed completed report will be required to be sent to the Data Coordinating Center within 3 working days of the event, and the medical monitor will assess all serious adverse events reported from site investigators.

For each of these serious adverse events, the site investigator will provide sufficient medical history and clinical details for a safety assessment to be made with regard to continuation of the trial. The medical monitor will sign off on each SAE report after review. All SAE reports will be retained at the Data Coordinating Center, and all SAE reports will be available for review by funding staff. The SAE reporting process may be incorporated into the Electronic Data Capture (EDC) System in use for the study.

In the unlikely event that the medical monitor believes an unexpected and study-related SAE warrants emergent cessation of enrollment in the trial, funding staff will be immediately consulted. If these individuals concur with the judgment of the medical monitor, or if the funding staff cannot be reached expeditiously, the Data Coordinating Center will notify the study investigator and all site investigators to cease enrollment in the trial. Resumption of enrollment will not occur without consent of the funding staff.

In accordance with local IRB requirements, the site investigator may be required to report such events to the IRB in addition to notifying the Data Coordinating Center.

6.1.9 Follow-up of Serious, Unexpected and Related Adverse Events

All serious, unexpected and related adverse events, that are unresolved at the time of the patient's termination from the study, will be followed by the site investigators until the events are resolved, subject is lost to follow-up, the adverse event is otherwise explained or has stabilized, or 12 months have passed from the time of last study dose.

7 Assessment of secondary endpoints

1. Re-epithelialization will be graded by trained, masked examiners on days 1, 3, 4, 5, 6, 7, and 8 unless patient re-epithelializes sooner in which case they can skip visits until day 8. Dimensions of the epithelial defects will be directly measured using slit lamp bio-microscopy. The baseline epithelial defect will be measured by surgeons on Day 1 at the time of surgery. Examiners will be masked as to which patients are using pAF vs. placebo. A vertical and horizontal measure of defect in mm will be performed, and defect area calculated. A complete re-epithelialization (absence of a defect) is defined when the measures equal zero.
2. Pain will be measured through a 0-10 scale on days 1, 2, 3, 4, 5, 6, and 7. Participants will rate their peak pain at the end of each day and directly return the forms at their in-person visit on day 8 to the examiners. They will complete a separate survey for each eye.
3. Uncorrected visual acuity will be measured at post-operative day 8, months 1, 3, 6, and 12 by trained physicians.
4. Manifest refraction and best-corrected visual acuity will be measured at months 1, 3, 6, and 12 by trained physicians.
5. Ocular surface staining will be measured at post-operative months 1, 3, 6, and 12 using an area density index.²⁵ This is a published and validated index used to measure corneal staining. Corneal regularity will also be measured at months 1, 3, 6, and 12 with the Surface Regularity Index (SRI) obtained via Zeiss Atlas 9000 Corneal Topography™.

8 Other Medications

- Oral pain medications usage will be tracked for the first 7 days.

9 Patient Withdrawal From Study

- A subject may withdraw their consent at any time without affect to their care.

10 Discontinuation of Study Drug

The study drug will be discontinued if any of the following occur:

- Development of severe ocular infection.
- Any other condition that in the opinion of the treating physician and ophthalmologist are not compatible with participation in this study.

11 Discontinuation of Study

- Any ocular serious, related and unexpected adverse effect that occurs in 1/3 of the patients (e.g. 1 out of 3, 2 out 6, 3 out of 9, etc.)
- The determination of the number of patients having serious, related and unexpected ocular adverse events in the study group will be reviewed by the DSMB, who may be unblinded to the study drug. Thus, the blind will not be broken throughout the study.
- The purpose of the DSMB is to advise the study investigators regarding the continuing safety of study subjects and the continuing validity and scientific merit of the study.
- The DSMB Chairperson will prepare a summary of each DSMB meeting that conveys the public conclusions of the DSMB, with respect to protocol alterations and recommendations concerning continuation of the study.
- In the unlikely event that the medical monitor believes an unexpected and study-related SAE warrants emergent cessation of enrollment in the trial, staff and the DSMB chairperson will be immediately consulted. If these individuals concur with the judgment of the medical monitor, or if the staff and the DSMB chairperson cannot be reached expeditiously, the DCC will notify the study investigator and all site investigators to cease enrollment in the trial. Resumption of enrollment will not occur without consent of the staff after discussion with the DSMB.

12 Statistical Considerations

12.1 General Statistical Methods:

Simple descriptive statistics of patient characteristics, operation parameters, and vision/ocular measurements will be calculated (overall and by pAF eye drop group vs. controls) at baseline, post-op and each follow-up visit. Outcomes will be described using appropriate summary measures and graphical approaches.

Between-group comparisons will be performed on:

- Time to complete re-epithelialization (primary efficacy outcome).
- Visual Acuity (best-corrected and uncorrected) (this measure at 30 days is the key secondary efficacy outcome).
- Dimensions of the epithelial defects directly measured using slit lamp biomicroscopy (exploratory efficacy outcome).
- Pain in each eye using a 0-10 point VAS scale on days 1, 2, 3, 4, 5, 6, and 7. (exploratory efficacy outcome).
- Timing and frequency of use of rescue pain medication.
- Corneal staining and surface irregularity.
- Adverse event rate and complication rate.

For the primary efficacy outcome, a mixed effects model with time to healing as outcome and assigned treatment arm as a predictor, including a random effect for each patient to model correlation between eyes in the same participant, will be fit to carry out the primary analysis. A two-sided probability value with an alpha level of 0.05 will be used to test the null hypothesis that time to complete re-epithelialization is not different between the two treatment arms. The primary analysis will be performed on an intention to treat basis.

12.2 Analyses for Other Outcomes:

The key secondary efficacy outcome at 30 days will be analyzed (on a logarithmic scale) using a mixed effects ANOVA model as for the primary aim. Exploratory outcomes will be analyzed in appropriate fashion; for example, each patients pain level (worst in either eye) will be examined on each evaluation day and compared between treatment groups for each day, while each patients peak pain level at any time, and number of days until the patient is pain-free, will be compared

between treatment arms. A Statistical Analysis Plan will fully delineate all analyses to be performed, including additional analyses to assess robustness of the primary and secondary efficacy analyses.

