6.1.2 Classification of an Adverse Event (Relatedness, Severity, and Expectedness)

Relatedness: The suspected relationship between study interventions and any adverse event will be determined by the site investigator using the criteria below. Relatedness must be assessed by an investigator and may not be assessed by a research coordinator.

- Not Related: The event is clearly related to other factors, such as the subject's clinical state, therapeutic interventions, or concomitant drugs administered to the subject.
- Possibly Related: The event follows compatible temporal sequence from the time of beginning the assigned study intervention, but could have been produced by other factors such as the subject's clinical state, therapeutic interventions, or concomitant drugs administered to the subject.

- Probably Related: The event follows a reasonable temporal sequence from the time of beginning the assigned study intervention, and cannot be reasonably explained by other factors such as the subject's clinical state, therapeutic interventions, or concomitant drugs administered to the subject.

Severity:

The severity, which is a measure of intensity, of clinical adverse events and laboratory abnormalities will be recorded by the site investigator and categorized. The following guidelines will be used to describe severity.

- Mild: The event requires minimal or no treatment and does not interfere with the participants daily activities.
- Moderate: The event results in a low level of inconvenience or concern with the therapeutic measures. Moderate events may cause some interference with functioning.
- Severe: The event interrupts a participants usual daily activity and may require systemic drug therapy or other treatment. Severe events are usually potentially life-threatening or incapacitating. Of note, the term "severe" does not necessarily equate to "serious".

Expectedness of the Event:

All adverse events, including serious adverse events, will be evaluated as to whether their occurrence was expected or unexpected. An AE will be considered unexpected if the nature, severity, or frequency of the event is not consistent with the risk information described for the study intervention. The following events will be reported as AEs::

- Infection
- Delayed healing of the epithelial defect (after the 7-day post-surgery visit)
- Scarring or haze
- Severe irritation of conjunctiva or periocular skin in the first week

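### Cheap improvement (low severity): the written study-halt provisions cover only unexpected events, so section 11 should say that a serious, related ocular infection or immune reaction counts whatever its expectedness label.

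*Protocol*

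**What the plan says.** Protocol section 11 gives one numerical stopping rule for the study: "Any ocular serious, related and unexpected adverse effect that occurs in 1/3 of the patients". Its worked examples are 1 of 3, 2 of 6 and 3 of 9. The next bullet sets the count behind the rule: "The determination of the number of patients having serious, related and unexpected ocular adverse events in the study group will be reviewed by the DSMB". The last bullet gives the medical monitor an emergency route: if that physician "believes an unexpected and study-related SAE warrants emergent cessation of enrollment in the trial, staff and the DSMB chairperson will be immediately consulted". Section 6.1.8 opens its own version of that route in the same terms: "In the unlikely event that the medical monitor believes an unexpected and study-related SAE warrants emergent cessation of enrollment in the trial". Section 6.1.7 has a further suspension route, for unanticipated problems, which are unexpected by definition.

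Expectedness, judged against the risks set out for the intervention, is defined in 6.1.2: "An AE will be considered unexpected if the nature, severity, or frequency of the event is not consistent with the risk information described". That subsection also puts infection first in its list of reportable events, and then says that infection is a theoretical risk of the drops and that an immune reaction could occur. Section 14.3 says there are no known or anticipated additional medical risks.

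Some provisions do not depend on expectedness. Section 6.1.8 says "the medical monitor will assess all serious adverse events reported from site investigators". SAP 5.1.1 has the DSMB review safety data at about 5, 30 and 60 randomized patients, with extra meetings if it wishes. Section 10 stops study drug in a patient with severe ocular infection.

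**The concern.** Safety is the primary objective, the patients are having elective surgery, and section 3.3 reports only three patients treated with pAF for an eye condition. Infection and immune reaction are the harms most specific to this product. They are also the two that 6.1.2 names, without saying how severe or how frequent a case would have to be to fall outside the described risk. An assessor working from nature alone could call a first case expected. It would then fall outside the one-third trigger, the DSMB count, both emergency-halt clauses and 6.1.7.

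The rule is meant to act on very few patients, since its first example is 1 of 3. At that point one label can decide whether it is met. Expectedness is a sensible filter for expedited reporting. It is a weaker filter for stopping, because a serious, related infection harms the patient equally whether or not it was foreseen.

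**Working it through.** **1. Does the wording leave room for an *expected* label?** Three passages bear on a serious, related infection or immune reaction:

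- Section 6.1.2 names both as possible with the drops. This points to *expected* on nature.
- Sections 6.1.2 and 3.3: neither sentence on the two risks describes a serious event, and 3.3 reports no directly associated adverse events in over 2000 applications. This points to *unexpected* on severity and frequency.
- Section 14.3 anticipates no additional medical risks. This points to *unexpected*.

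The definition is met if any one of nature, severity or frequency is inconsistent, so *unexpected* is the better reading. No sentence makes it certain.

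**2. The rule's own figures.** 1/3, 2/6 and 3/9 each equal one third, so the worked examples reproduce. A lone event meets the rule when 1/n ≥ 1/3, that is, when n ≤ 3. Otherwise the number needed is n/3 rounded up: 2 at n = 4 or 5, 5 at 15, 10 at 30, 20 at 60.

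**3. Size, with the pAF arm as denominator.** Assumptions: *study group* in the second bullet means the pAF arm; allocation is 1:1; the rule is applied only at the SAP looks, giving about 3, 15 and 30 pAF patients and thresholds of 1, 5 and 10. The serious-related event rate p is assumed, because the documents give none. For illustration, a lone first event is labelled expected and all events count once a second occurs. The first look then needs 2 of 3 in place of 1 of 3.

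- Lone event counts: P(X ≥ 1) = 1 − (1 − p)³
- Lone event left out: P(X ≥ 2) = 3p²(1 − p) + p³

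At p = 5%: 1 − 0.95³ = 0.143, against 3(0.0025)(0.95) + 0.000125 = 0.007.

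| Assumed rate | Lone event counts | Lone event left out |
|---|---|---|
| 5% | 14% | 0.7% |
| 10% | 27% | 3% |
| 20% | 49% | 10% |
| 1/3 | 70% | 26% |

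At the 30-patient look both versions need 5 of 15, so nothing changes (60% at a rate of one third either way). Over all three looks at a rate of one third, the chance falls from 86% to 73%.

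**4. Size, with all patients as denominator.** The first bullet says only *patients*. On that reading the looks at 5, 30 and 60 need 2, 10 and 20 events. Every threshold is at least 2, so under the same labelling assumption the difference is zero at all three looks. A lone event would matter only if the rule were checked within the first three patients enrolled.

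**5. Sensitivity after the change.** With 3 pAF patients, P(X ≥ 1) is 3%, 14% and 27% at assumed rates of 1%, 5% and 10%. With 2 pAF patients it is 1 − (1 − p)², or 2%, 10% and 19%. Later looks add less than 1 percentage point at these rates. These are totals: events already classed as unexpected count today.

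**The case against.** The strongest reply is that the plan already gives the right answer. The definition of *unexpected* is broad, and 3.3 and 14.3 both push a serious, related case into it. Risk information outside the protocol and SAP, such as the consent form, may settle the matter and was not available here. Nor would a case labelled expected go unseen: the medical monitor assesses every SAE with continuation of the trial in mind, and the DSMB sees safety data, can call ad hoc meetings and can ask to be unblinded. The emergency halt turns on what the monitor believes, and nothing binds the monitor to a site's label. All of this stands, and it is why the point is of low severity. What remains is that these routes are discretionary and the written triggers are not explicit.

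A reader might infer three stronger points, none of which the documents support:

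- *That serious infections are excluded from stopping.* They are not. The better reading counts them, and a cluster would most naturally be unexpected on frequency.
- *That nobody assesses expectedness.* Section 6.1.2 does use the passive: "All adverse events, including serious adverse events, will be evaluated as to whether their occurrence was expected or unexpected". But 6.1 makes the site investigator responsible for evaluating all adverse events, and the two read together name an assessor.
- *That* unexpected *should be deleted throughout.* Section 11 does not say whether *related* includes the weakest category, "Possibly Related: The event follows compatible temporal sequence from the time of beginning the assigned study intervention". If it does, deletion could let one PRK complication judged serious meet the rule at 1 of 3. That trade-off is debatable and is not needed to close the gap.

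**Conclusion.** The point holds as a low-severity wording improvement. Every written study-level halt provision requires an unexpected event, and the text permits, without favouring, an *expected* label for a serious, related infection or immune reaction. The consequence is limited to the written triggers, because review by the medical monitor and the DSMB continues either way.

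For the one-third trigger the effect is early and partial: about 14% against 0.7% at an assumed 5% rate with 3 pAF patients, none at the 30-patient look, and none at any planned look if all patients are the denominator. The event rates and the labelling pattern are assumptions used for illustration, and the documents support neither as a prediction. Once more than three patients are in the denominator, a lone event misses the one-third fraction whatever its label. The gain then lies in the DSMB count and the emergency halt.

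**What to change.** Add to Protocol section 11, with a cross-reference in 6.1.8:

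> Any serious, related ocular infection or immune reaction counts towards this rule, the DSMB count and the emergency halt regardless of expectedness.

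Keep the one-third fraction. Leave *unexpected* in place for all other events, for reporting and for the definition in 6.1.7.

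The cost is one sentence and a cross-reference, using adverse event data and a DSMB that already exist. Section 15.4 requires an amendment with IRB approval, and FDA review if the change is judged to affect subject safety significantly. The downside is a slightly more sensitive early trigger. The totals in step 5 of the working show the scale, with the rate now being that of the two named events for cases not already classed as unexpected. The safety record in section 3.3 points to the low end of that range, although only three of those patients were treated for an eye condition. Limiting the sentence to infection and immune reaction largely keeps ordinary PRK complications out, but an infection linked to the drops by timing alone could still count if *related* includes possibly related.

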12.3 Statistical Power and Sample Size: Time to complete re-epithelialization

Time to complete re-epithelialization will be measured from the end of surgery until the date of the exam where complete re-epithelialization is observed. While evaluation times will be collected, since the time of surgery and the time of the follow-up exam are dependent upon scheduling, time to complete re-epithelialization will be analyzed as an integer, being simply the number of calendar days from the day of surgery to the date of the first examination demonstrating complete re-epithelialization.

12.4 Sample Size calculations for pAF PRK study

A mixed effects ANOVA model for difference in time to complete re-epithelialization was used to determine sample size. A within-subject correlation in healing times of $r = 0.5$ was assumed. Calculations were performed to achieve a power of 80% and 90% and a level of significance of 5% (two sided).

12.5 Sample size calculations:

Eliacik et al.,²⁶ found a mean time to re-epithelialization of 3.1 ± 0.6 days for the Comfilcon Group and 3.6 ± 0.5 days for the Lotrafilcon Group. We used this 0.5-day difference as an estimate of treatment effect, and considered within-group standard deviations in the range of 0.5 to 0.7 days. Another key parameter in the estimation of statistical power is the intraclass correlation between eyes in the same patient. This correlation was estimated to be in the range of 0.5 to 0.75, as within-patient healing times have been reported to be nonuniform to a modest extent in the study PIs experience. The table below shows true treatment differences detectable with 80% and 90% power under different estimates of the variability of re-epithelialization time and intraclass correlation, **assuming that 56 participants (28 participants and therefore 56 eyes in each treatment arm) complete the trial.** These values were calculated using PASS [PASS 15 Power Analysis and Sample Size Software (2017). NCSS, LLC. Kaysville, Utah, USA, [ncss.com/software/pass.](http://ncss.com/software/pass/)], treating the study as a cluster-randomized trial with clusters (each participants eyes) of size two.

| Assumed Within-Group Standard Deviation of Primary Outcome | Assumed ICC between a Participants Eyes | Treatment Difference Detectable with 80% Power | Treatment Difference Detectable with 90% Power |
|--|---|--|--|
| 0.5 days | 0.5 | 0.33 days | 0.38 days |
| 0.5 days | 0.6 | 0.34 days | 0.39 days |
| 0.5 days | 0.75 | 0.35 days | 0.41 days |
| 0.6 days | 0.5 | 0.39 days | 0.45 days |
| 0.6 days | 0.6 | 0.41 days | 0.47 days |
| 0.6 days | 0.75 | 0.42 days | 0.49 days |
| 0.7 days | 0.5 | 0.46 days | 0.53 days |
| 0.7 days | 0.6 | 0.47 days | 0.55 days |
| 0.7 days | 0.75 | 0.49 days | 0.57 days |

Based on numerous power estimates (the above and others), a sample size of 56 patients completing the trial, yields acceptable power to find a significant treatment difference, if the true treatment difference is at least 0.5 days for the time to complete re-epithelialization outcome. In order to collect additional safety data and allow for a small number of patients being lost to follow-up, the study will enroll a total of 63 participants.

